1. PURPOSE OF STUDY

Our research group developed a new youth-centered module (YM) for the previously validated Youth-nominated Support Teams (YST) intervention, a broader program to prevent re-attempts among adolescent suicide attempters. As part of the principal investigator's KL2 award, we propose a one-armed pilot trial to optimize and evaluate the feasibility, acceptability, and target engagement achieved by adding this module (YST+YM) to the existing intervention. This pilot trial ("study") will proceed in two phases. Phase one (content refinement): we will optimize the YST+YM intervention for feasibility and acceptability (n = 5-10); phase two (pilot): we will conduct a within-subjects pilot trial to test target engagement (social support) with this population (n = 60-70).

2. BACKGROUND AND RATIONALE

Adolescent suicide rates have increased 44% since 2000, and suicide is now the 2nd leading cause of death for youth ages 14-25.¹ Adolescents hospitalized for suicide attempts (ASAs) are a uniquely high risk subgroup: 30% reattempt suicide within a year of discharge.^{2,3} Current interventions for ASAs are predominantly individual treatments, which meta-analysis shows reduce adolescent suicide attempts by less than 9%.⁴ In contrast to these individual-centered approaches, numerous studies demonstrate that key suicide risk factors (e.g., depression,⁵ emotion dysregulation,⁶ outpatient treatment adherence ⁷) are influenced by social networks - including the peer and adult relationships in which adolescents are already embedded.^{8–12}

Overview of traditional YST. The Youth-nominated Support Team (YST)^{13,14} is an established intervention for ASAs leaving acute treatment. YST is a supplemental intervention, designed to be added onto normal post-discharge treatment as usual (e.g., outpatient psychotherapy). Patients randomized to YST show a roughly 50% reduction in mortality (all-causes, not just suicide) over 10 years after the intervention, compared to patients discharged to outpatient therapy alone.¹⁵ YST begins roughly one week before discharge from psychiatric hospitalization. At this time, the ASA subject nominates 3-4 trusted adults they already know who will provide social support to the patient for the 12 weeks following discharge. Those adults then receive psychoeducation on the ASA's mental health concerns, as well as weekly check-ins from a trained mental health provider to help those adults troubleshoot any issues with their support role for the ASA. Note, these adults are explicitly told to provide only social support. They do not provide clinical treatment or crisis management as part of YST. Those roles are already fulfilled by each youth's outpatient psychotherapist. Being enrolled in outpatient therapy is a precondition for participating in YST.

Limitations of traditional YST. Despite its established reductions in mortality, YST is limited in that it contains no direct content for the patient at the center of the intervention. In traditional YST, once the patient has nominated their trusted adults, no additional intervention is conducted with the patient - the intervention subsequently targets the behavior of the supportive adults only. These adults are the only ones who receive any contact, psychoeducation, or check-ins with study staff. This leaves multiple social needs of the adolescent unaddressed, such as the need to develop proactive help-seeking skills and the effective utilization of the social support that is now available to them.

Page 2 of 64 Version Date: 12/13/21 **Overview of the study and the proposed YST+YM intervention.** This investigation proposes a two-phased, one-armed pilot trial to optimize and evaluate the addition of a new youth-centered module (YM) to the traditional YST intervention (i.e., a pilot trial of YST+YM). This module was produced in consultation with YST's creator, [name]^{13–15} and revised with feedback from the Department of Psychiatry Advisory Council of Consumers (DPACC), as well as with feedback from patients from the Child and Adolescent Partial Hospital Service (CAPHS) at the University of Rochester Medical Center.

YST+YM will include **everything in traditional YST**, **plus three one-hour patient-involved sessions** designed to help the ASA set goals for the 12-week post-discharge period and to strategize how they want to utilize the support from their adult team. The first of these sessions will occur prior to discharge and will be either in-person or administered remotely, depending on current URMC policy. The rest of the intervention - mirroring traditional YST - will be entirely remote and conducted either via phone or Zoom. Based on feedback from adolescents in the CAPHS program, patients participating in YST+YM will also receive **weekly automated text messages** asking basic questions about their progress and providing them with encouragement to continue regular contact with their adult support team members. About two thirds of these text messages will be **group text messages** that include both the youth and at least one member of their support team. These multi-person text messages will be designed to prompt co-reflection on healthy relationships and behaviors, consistent with the interventions themes.

Specific Aims & Hypotheses:

Aim 1 - To optimize YST+YM for feasibility and acceptability. Outcome: Semi-structured interviews and rating scales will identify the most and least preferred elements of the YM module. Response rates to automated text-messages will also be used to evaluate message appeal.

Aim 2 - To test target engagement: does YST+YM increase utilization of interpersonal emotionregulation strategies and social support among adolescents with recent suicidal ideation or attempts? Hypothesis: over 12 weeks of YST+YM, subjects will demonstrate increases in: (a) the number of weekly contacts initiated to supportive adults in their lives, (c) the utilization of interpersonal emotion regulation strategies, and (c) their perceived sense of social support. These gains will be maintained at 3-month post-intervention follow-up.

Aim 3: Estimate prevalence of clinical outcomes for planning of subsequent trials - what is the average rate of clinical over the course of intervention and through 3-month follow-up? Outcome: Estimates of changes in distal targets, including anxiety, depression, and suicidal ideation and attempts for the planning of larger subsequent trials.

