6. INCLUSION AND EXCLUSION CRITERIA

Page 5 of 64 Version Date: 12/13/21

Youth subjects:

Subjects will be **included** if:

- Youth subject is being discharged from the Child and Adolescent Partial Hospital Service (CAPHS) in the URMC Department of Psychiatry.
- Youth subject endorses past year suicide attempt OR past year suicidal ideation at time of partial hospitalization, as assessed on standardized intake questionnaire used by CAPHS.
- Youth subject has a cellular phone, with an active service plan, that is capable of sending and receiving standard SMS text messages.
- Youth subject is aged 12 18 at time of enrollment.

Subjects will be **excluded** if:

- Youth subject has medical or psychiatric comorbidities that impair ability to assent (e.g., active psychotic or manic episode, cognitive impairment).
- Youth subject patient or guardian does not speak fluent English, as meeting translation costs is not possible in this study.
- Youth subject is unable to name at least 2 trusted adults (at least 1 of which is not a parent or caregiver) they would like to serve on their support team.
- Youth is unable or unwilling to share their suicide-related safety plan

Parent / legal guardian subjects:

Subjects will be included if:

• Adult subject is at least 21 years of age.

Adult support team subjects:

Subjects will be **included** if:

- Adult subject is nominated by a youth subject to serve on their adult support team
- Adult subject is approved by youth subject's parent or legal guardian
- Adult subject has a cellular phone, with an active service plan, that is capable of sending and receiving standard SMS text messages.
- Adult subject is at least 21 years of age.

Subjects will be **excluded** if:

- Adult subject has medical or psychiatric comorbidities that impair ability to consent (e.g., active psychotic or manic episode, cognitive impairment).
- Adult subject does not speak fluent English, as meeting translation costs is not possible in this study.
- Adult reports being unable to be in contact with youth at least once per week, for the 12 weeks of the intervention

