7. RECRUITMENT METHODS

Over the past year, the Department of Psychiatry's Child and Adolescent Partial Hospitalization Service (CAPHS) already piloted traditional YST to evaluate the feasibility and acceptability of incorporating it into regular clinical care. Consultation with [name] (LCSW-R, Director of CAPHS) revealed their existing recruitment procedure for traditional YST was both efficient and acceptable for clinic staff, patients, and their caregivers. The current recruitment procedure is designed to be consistent with CAPHS' previously successful approach. Phases one and two will utilize the same recruitment procedure.

Youth patient identification: All CAPHS therapists will receive a verbal overview of the study,

prior to its implementation. When the study is active, CAPHS therapists will ask their patients with recent suicide concerns (see inclusion criteria) whether they are interested in participating in a post-discharge study. This introduction will occur during normal clinical interaction. Therapists will attempt to time the introduction to be within approximately one week of the patient's expected discharge from CAPHS. If the patient expresses interest during this initial introduction, and confirms to the therapist that they can name two trusted adults they believe would be interested in serving on their support team, the therapist will notify study staff of the patient's interest.

Youth screening: When a CAPHS therapist notifies study staff of an interested patient, study staff will confirm with the therapist that the patient meets study inclusion and exclusion criteria. Consultation with CAPHS therapists confirms they reliably have the information needed to confirm inclusion or exclusion, as this information consistently arises as part of their normal assessment and treatment process with patients.

Importantly, although we will collect clinical information from these therapists for purposes of subject screening, the therapists themselves are not engaged in formal research. Any information we receive from the therapists will be used for screening purposes only and will not be analyzed as part of the study.

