Semi-structured feedback interview Format: Staff-administered Recipients: Youth only Administered (4x): During the three intervention sessions, follow-up (week	• Open-ended feedback: Three questions designed to invite feedback from the subject, including intervention content subjects want to change in the future, what they would want to retain, and their overall impressions of the program.

22-24) Approx. duration: 15-20 mins	
Columbia Suicide Severity Rating Scale (C- SSRS) Format: Staff-administered Recipients: Youth only Administered (4x): Immediately following each Youth Social and Emotional Survey (i.e., after the three intervention sessions, and once at follow-up – week 22-24) Approx. duration: 5 mins	 Suicide risk assessment: Administered to all youth following all social and emotional surveys, the C-SSRS asks a series of questions about recent suicidal thoughts and behavior in plain language. Only administered to youth who screen positive on Social and Emotional Survey for current suicidal planning

The study intervention consists of two components: the already established Youth Support Team (YST) intervention that provides education and check-ins for the adults on the support team and a Youth-centered Module (YM) that includes 3 remote sessions involving the youth and weekly text messages. The timeline for each component is described below.

Youth Support Team (YST): As soon as a given supportive adult agrees to serve on a subject's support team, study staff will schedule a psychoeducation session (45-90 minutes). This session will be conducted remotely via HIPAA-compliant video conference and includes information about how to provide social support to youth with psychiatric symptoms. Adults are reminded their only role is to provide social support (not clinical assessment or care), but they are still provided with information on how to handle any safety concerns with the adolescent that may arise. Each adult on the support team is instructed to remain in active contact with the youth at least once a week. Adults also receive weekly 3-15 minute check-in calls from study staff for 12 weeks to help them optimize the social support they provide.

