12. POTENTIAL BENEFITS TO SUBJECTS

In a similar study population of acutely suicidal adolescents, traditional YST reduced all-cause mortality by 50% over the subsequent 10 years.¹⁵ Because our study intervention (YST+YM) includes a full administration of traditional YST, it is likely some youth subjects may experience reduced risk of suicide attempt or longer term risk of all-cause mortality as a result of participation in the study. Because the study intervention further targets social support surrounding youth, which is known to have anti-depressive and anti-anxiety effects, youth subjects may also experience improved mood and emotional state over the course of the study.²⁻⁵ There are no direct benefits of the intervention for parents / legal guardians or adult support team subjects. For all subjects, it is possible the assessment portion of this study may

Page 18 of 64 Version Date: 12/13/21 provide benefit by facilitating subjects' learning about themselves.

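### Outpatient therapy is called a precondition for YST, which YST+YM contains in full, but no youth eligibility criterion in section 6 requires it

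*Combined protocol and SAP*

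**What the plan says.** Section 2 (Overview of traditional YST) describes how responsibilities are divided in the parent programme. Of the support adults it says: "They do not provide clinical treatment or crisis management as part of YST". It continues: "Those roles are already fulfilled by each youth's outpatient psychotherapist". It then states the entry rule: "Being enrolled in outpatient therapy is a precondition for participating in YST".

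The same section says that YST+YM will include "everything in traditional YST" plus the new youth sessions. Section 12 repeats this: "our study intervention (YST+YM) includes a full administration of traditional YST". Section 9 (Youth Support Team) restates for this trial that the adults' role is social support and not clinical assessment or care.

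Section 6 lists the youth criteria. The first inclusion criterion is "Youth subject is being discharged from the Child and Adolescent Partial Hospital Service (CAPHS) in the URMC Department of Psychiatry". The others concern past-year attempt or ideation, a phone that can send and receive text messages, and age. The exclusions concern ability to assent, fluency in English, naming trusted adults, and sharing the safety plan.

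On screening, section 7 says "study staff will confirm with the therapist that the patient meets study inclusion and exclusion criteria". Table 2 in section 9 describes the child pre-screening form by pointing back to the same criteria.

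**The concern.** The precondition is the stated reason why lay adults can safely be limited to social support: a clinician outside the study handles treatment and crises. This trial keeps the limit on the adults but does not turn the condition behind it into an eligibility rule. Staff screen from section 6, not from the background section, so the condition may never be checked.

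The population has a past-year suicide attempt or suicidal ideation and is entering the post-discharge period. Part of the risk response in section 11 also assumes an outside clinician: its listed steps include contacting the therapist or primary care provider, and providers are to be told of elevated risk. For a youth with no therapist, that part of the response is weaker. Table 2 lists no measure of whether a youth is in outpatient therapy, so on the visible plan the gap would not show up afterwards either.

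**Working it through.** This is mainly a comparison of texts. The arithmetic at the end only illustrates scale.

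**1. Does the precondition carry over?** Section 2 states it for traditional YST. Sections 2 and 12 say YST+YM delivers all of YST, and section 9 keeps the adults' restricted role. The reason for the precondition therefore applies here unchanged.

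**2. Is it in section 6?**

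| Youth criterion | Requires outpatient therapy? |
|---|---|
| Inclusion: CAPHS discharge | No |
| Inclusion: past-year attempt or ideation | No |
| Inclusion: SMS-capable phone | No |
| Inclusion: age 12 to 18 | No |
| Exclusion: comorbidity impairing assent | No |
| Exclusion: youth or guardian not fluent in English | No |
| Exclusion: cannot name at least 2 trusted adults | No |
| Exclusion: cannot or will not share safety plan | No |

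**3. Is it anywhere else?** The recruitment, consent, procedures, risk, withdrawal and monitoring sections contain no such requirement. Sections 2 and 11 presume treatment as usual after discharge, but nothing says that CAPHS discharge guarantees outpatient therapy. The discharge requirement that is stated (section 8 and the data and safety monitoring section) is a safety plan. Lack of outpatient care is not a withdrawal reason in section 15.

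**4. Illustration of scale.** Section 5 gives about 165 screened, more than 80% eligible, 50% of those enrolling, and 65 enrolled. Checking the plan's own figures: 165 × 0.80 = 132 (stated as 130), and 130 × 0.50 = 65.

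Let x be the number per 100 CAPHS patients who meet section 6 but have no outpatient therapy. The documents do not give x; 0, 5 and 10 are assumed, with the same 50% uptake.

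- Enrolled youth without therapy = 65 × x/80
- Number to screen to enrol 65 with the criterion added = 65 / (0.50 × (0.80 − x/100))

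| x (assumed) | Enrolled without therapy | Screened with the criterion | Extra screened |
|---|---|---|---|
| 0 | 0 | 65/0.400 = 162.5 | 0 |
| 5 | 65 × 5/80 = 4.1 | 65/0.375 = 173.3 | 10.8 |
| 10 | 65 × 10/80 = 8.1 | 65/0.350 = 185.7 | 23.2 |

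**The case against.** The strongest reply is that the sentence is background on the parent programme, and that carrying over all of YST most naturally means its components, not its entry rules. On the other reading, if section 2 does govern this trial, the rule is already stated and has only not been repeated. Aftercare also looks likely in practice. Section 11 describes treatment as usual as recommended and implemented by CAPHS staff. The only route into the study is the youth's CAPHS therapist, who also attends the consent session. Recruitment follows a year in which the clinic ran traditional YST. The risk response does not depend on a psychotherapist: a primary care provider satisfies the contact step, and mobile crisis, emergency services and hospitalization are also listed. The pre-screening form and the attached Data and Safety Monitoring Plan were not available for this review and might cover the point.

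Much of this stands, and it lowers the chance that a youth without a therapist is enrolled unnoticed. The illustrative figures carry no evidential weight. No aim, model or power statement is affected.

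It does not close the gap. Whichever way section 2 is read, the rule is missing from the list that staff apply, and nothing visible guarantees or verifies outpatient therapy. The reason for the precondition holds in this trial even if the sentence was written about the parent programme.

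**Conclusion.** The concern holds. Section 6 applied as written admits a youth whom the protocol's own safety rationale would exclude. Confidence is high on the omission. How often it would matter is unknown: the documents give no figure, and if CAPHS always arranges outpatient therapy the answer is zero. The range of 0 to about 8 of 65 enrolled youth rests wholly on the assumed 0 to 10 per 100 and is not a bound.

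One safety layer is at stake, not the whole safety plan. The shared safety plan, review of survey responses straight after each assessment, C-SSRS items, senior review and crisis services all remain. The change should be made, but the omission does not undermine the design or analysis.

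**What to change.** Add a youth inclusion criterion to section 6: at CAPHS discharge, the youth is enrolled in outpatient therapy or has a confirmed intake appointment for it. The appointment option is looser than the wording in section 2, but eligibility is checked and consent given before discharge, when therapy may not have started. Add a matching item to the child pre-screening form, answered by the referring CAPHS therapist, unless the form already has one.

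The cost is one protocol line and one question to someone who already confirms eligibility. The estimate of more than 80% eligible may fall slightly, by an amount the documents do not give. Under the assumed 5- or 10-point fall, the number screened rises from about 163 to about 174 or 186, which is 11 or 23 more. If therapy is universal at discharge, the criterion excludes nobody.

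This settles eligibility at entry only. It does not deal with therapy that lapses during the 12 weeks.

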4. STUDY DESIGN

This study is a two-phased, one-armed pilot trial to evaluate feasibility, acceptability, and target engagement of YST+YM. It will also facilitate estimation of clinical outcome prevalence, including suicidal ideation and attempts over the intervention period and through post-intervention follow-up.

In phase one (content refinement; n = 5-10), feasibility and acceptability will be optimized via measures of subject engagement with the intervention (i.e., text-message response rates) and with subject feedback during semi-structured interviews. We will also assess feasibility of the assessments used to measure emotion regulation, perceived social support and connectedness, and clinical outcomes (i.e., anxiety, depression, and suicidal ideation and attempts).

In phase two (pilot; n = 60-70), target engagement and prevalence of clinical outcomes will be addressed, as well as continued assessment of feasibility and acceptability of YST+YM. Consistent with specific aims above, intervention targets include engagement with treatment (i.e., initiating contact with support team members), changes in emotion regulation skills, and perceived social support and connectedness. Distal targets, including anxiety, depression, and suicidal ideation and attempts will also be assessed to establish point estimates for power analysis and sample size planning in future trials. Subject engagement with the intervention and feedback during semi-structured interviews will be used to assess feasibility and acceptability of YST+YM (following initial modification in response to phase one subject feedback).

Because the intervention lasts approximately three months per subject, the phases will be staggered, such that some subjects will be enrolled in phase two before all phase one subjects have completed their entire intervention course. For example, we anticipate that n = 5-10 phase one subjects may complete the first remote session of YST+YM within 6 weeks of the study start date. Because we collect feedback immediately following each session, this means we will have received all the information required to finalize that session's outline and content for the launch of phase two – even though these phase one subjects will have several weeks left of YST+YM overall.

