5. SUBJECT POPULATION

Number of Subjects: This study includes three sets of subjects, including (1) youth patients, (2) parents, and (3) their respective adult support team members. The subject population is the same for both phases one and two.

• Youth patients: We will enroll approximately n = 60-70 total adolescent patients in the Child and Adolescent Partial Hospitalization Service (CAPHS). The first n = 5-10 of these will be used to refine and optimize the feasibility and acceptability of YST+YM. All

Page 4 of 64 Version Date: 12/13/21 subjects will be used to evaluate target engagement. Based on consultation with CAPHS clinical director, [name] (LMSW-R), greater than 80% of patients are expected to be eligible for participation. Of eligible patients, roughly 50% are estimated to enroll in the study. Again based on consultation with [name], 75% of the initially enrolled patients are expected to complete the study. Thus, we will screen approximately 165 patients to identify 130 eligible subjects, of which 65 are expected to enroll. Given low attrition for comparable clinical programs in CAPHS (i.e., a year of pilot implementation of traditional YST in that clinic), we conservatively estimate a 25% attrition rate. Attrition will be handled with an intent-to-treat design. Given these considerations, we anticipate n = 50 subjects will provide follow-up data, providing a sufficient sample size to detect a signal for intervention target engagement.

- Parents / legal guardians: We will invite one parent / legal guardian per enrolled youth to provide feedback on the intervention, proxy-ratings of the youth's emotional well-being, as well as self-report of their own well-being. Based on consultation with clinic staff who regularly interact with this population, recruitment and retention rates for parents are expected to be roughly 80% per youth who completes the study. Thus, for the roughly n = 50 youth subjects who provide full follow-up data, we expect roughly n = 40 parents / guardians to complete all measures. This is a sample size sufficient to refine the intervention with informal feedback and to further evaluate target engagement as assessed by proxy-report.

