9. STUDY PROCEDURES

Phases one and two will utilize the same study procedures. Screening will occur via consultation with youth subjects' current therapists, who have all the necessary information to confirm youth eligibility as part of their normal clinical practice. Demographic information on youths who are screened, but determined to be ineligible, will be documented; however, no identifying information will be retained on these ineligible subjects.

After screening and signing assent / consent forms, study staff collect background information from subjects, such as demographics and nomination of 3-4 trusted adults to serve as their support team, via REDCap. Parents and guardians will be involved in the nomination process and must verbally approve all of the subject's adult nominees. Then, the baseline session is scheduled. This baseline session includes both the baseline assessment and initial session of the Youth-centered Module (YM) of the YST+YM intervention. Subjects have the option of completing this visit in-person or remotely, depending on current URMC and clinic policy. Those who complete it remotely do the baseline assessment and intervention via HIPAA-compliant video conference. After the baseline session has been scheduled with the subject, study staff will contact the subject's adult support team nominees, explain the intervention to them, and then confirm they are willing and able to serve as a support team member for the subject. Per subject need/request, URMC study staff will read aloud instructions and questions to aid their responding via tablet, phone, or computer. In the case that the REDCap site is down or malfunctioning, screening, assent / consent and questionnaires are completed on paper and later entered into REDCap.

Select questionnaires from the battery are re-administered at 6 weeks (mid-intervention), 12 weeks (immediately post-intervention), and 24 weeks (follow up). All of these assessments will be completed live (via HIPAA-compliant video conference) with study staff, who will review

Page 10 of 64 Version Date: 12/13/21 subject responses for safety concerns immediately after the assessment is completed. Table 1 depicts the assessment timeline for all subjects in the study. Table 2 provides the content of all the measures included in each assessment.

Table 1. Assessment timeline by subject type

		Post- discharge week				
	Pre-discharge	1-3	4 – 6	7-10	10-12	22-24

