Adult experiences and feedback survey Format: Self-report	 Identity confirmation: Name and date of birth for longitudinal linking survey linking in database Demographics (e.g., age, race, gender) Acceptability ratings and feedback: Custom rating scales and open-ended questions about intervention 			

Recipients: Parents, adult supports Administered (2x): After first session, Weeks 10-12 Approx. duration: 15-20 mins	 acceptability, time taken, and perceived benefits for child Child depression symptoms: PROMIS Parent Proxy Short Form v2.0 - Depressive Symptoms 6a Child life satisfaction: PROMIS Parent Proxy Short Form v1.0 - Life Satisfaction 4a Adult depression symptoms: PROMIS Short Form v1.0 - Depression 4a Adult general stress: NIH Toolbox Perceived Stress Fixed Form Age 18+ v2.0
Youth social and emotional survey Format: Self-report Recipients: Youth only Administered (4x): During the three intervention sessions, follow-up (week 22-24) Approx. duration: 30-60 mins	 Identity confirmation: Name and date of birth for longitudinal linking survey linking in database Demographics (e.g., age, race, gender) Acceptability ratings and feedback: Custom rating scales and open-ended questions about intervention acceptability and perceived benefits. Depressive symptoms: PROMIS Pediatric Short Form v2.0 - Depressive Symptoms 8a Suicidal thoughts and behaviors: Short Mood and Feelings Questions about recent and historic suicide attempts Social Connectedness: Interpersonal Needs Questionnaire – Belongingness subscale Feelings of meaning and purpose: Claremont Purpose Scale – Goal-directedness and Personal Meaning subscales Emotion Regulation: Interpersonal Emotion Regulation Questionnaire - Social Modeling Subscale, Difficulties in Emotion Regulation Scale – Regulation Strategies Subscale Engagement with healthy activities: Behavioral Activation for Depression – Short form – Activation Subscale Adult support team activities: Custom questions about frequency of contact with parents and team adults on intervention support team. Questions include content about different activities (e.g., help with homework, social support) and forms of interaction (e.g., in person, over the phone).

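### Aim 3 promises estimates of change in anxiety, but Table 2 lists no youth anxiety measure; the C-SSRS row of the same table also gives two conflicting rules for who is assessed

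*Combined protocol and SAP*

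**What the plan says.** **Anxiety.** The outcome statement for Aim 3 (Section 2, Specific Aims) is "Estimates of changes in distal targets, including anxiety, depression, and suicidal ideation and attempts for the planning of larger subsequent trials". Section 4 returns to this twice. For phase one, feasibility is to be assessed for the instruments measuring "clinical outcomes (i.e., anxiety, depression, and suicidal ideation and attempts", among others. For phase two, "Distal targets, including anxiety, depression, and suicidal ideation and attempts will also be assessed to establish point estimates for power analysis". Section 12 also cites an anti-anxiety effect of social support as a reason youths may benefit. Section 17 says Aim 3 will be reported as means and proportions kept for planning later studies.

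Section 9 states that "Table 2 provides the content of all the measures included in each assessment". In that table the youth survey has "Depressive symptoms: PROMIS Pediatric Short Form v2.0 - Depressive Symptoms 8a", and the parent and support-adult survey has "Child depression symptoms: PROMIS Parent Proxy Short Form v2.0 - Depressive Symptoms 6a". No row names an anxiety measure.

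**C-SSRS.** The C-SSRS row of Table 2 specifies four administrations, one directly after each youth survey, and says: "Administered to all youth following all social and emotional surveys, the C-SSRS asks a series of questions about recent suicidal thoughts". The same cell ends by restricting the scale to youths whose survey is positive for current suicidal planning. Table 1 does not list the C-SSRS. Section 11 says only that the safety protocol uses items from it together with a clinical interview.

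**The concern.** A pilot that is meant to supply planning values has to measure the outcomes it names. Without an anxiety scale there is no mean, SD or change score to carry into the next trial's sample-size calculation. The loss is permanent, because baseline scores cannot be obtained once youths have been discharged and treated. Section 4 also promises to test the feasibility of the anxiety assessment, which cannot be done if there is none.

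The C-SSRS conflict is operational. The study enrols 12- to 18-year-olds with suicidal ideation or an attempt in the past year, and staff reading one table cell find two instructions that cannot both be followed. Different staff could apply different rules. Under the restrictive rule, C-SSRS data would exist only for a selected subgroup and could not give whole-sample rates.

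**Working it through.** **1. Aim 3 outcomes set against Table 2.** This part is a comparison of text; the plan gives no figure to reproduce. The .82 power in Section 17 is for Aim 2, and the plan says none was computed for Aim 3.

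| Aim 3 outcome | Youth survey | Parent and support-adult survey | C-SSRS |
|---|---|---|---|
| Anxiety | none | none | no |
| Depression | PROMIS Pediatric 8a | PROMIS Parent Proxy 6a | no |
| Suicidal ideation | suicidality items | none | yes |
| Suicide attempts | suicidality items | none | yes |

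The other youth domains are belongingness, purpose, emotion regulation, behavioural activation and contact with adults. Emotion regulation is an Aim 2 target, not an anxiety measure. The adult survey adds child life satisfaction by proxy and the adult's own depression and perceived stress; the last is not youth anxiety. Result: 1 of 4 named outcomes has no instrument.

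**2. Number of surveys affected.** Inputs are 65 expected to enrol and, from Section 5, "we anticipate n = 50 subjects will provide follow-up data". Table 2 gives the youth survey four times. Assume that the 50 complete all four surveys and that each of the other 65 − 50 = 15 completes one to three.

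- Completers: 50 × 4 = 200
- Non-completers: 15 × 1 = 15 to 15 × 3 = 45
- Total: 215 to 245 (ceiling 65 × 4 = 260), with 0 anxiety scores

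Replacement of withdrawn youths (Section 15, Subject Withdrawals) is not counted.

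**3. What an added scale would give.** The 95% CI half-width for mean change from baseline to follow-up, in baseline SD units, is t × √(2(1 − r)) / √n. Here n = 50 and t(49, 0.975) = 2.010. The SD is assumed equal at the two times. The within-person correlation r is also an assumption, since the plan gives none.

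- r = 0.3: 2.010 × √1.4 / √50 = 0.336 SD
- r = 0.5: 2.010 × √1.0 / √50 = 0.284 SD
- r = 0.7: 2.010 × √0.6 / √50 = 0.220 SD

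This shows what adding a form would buy; it does not measure the defect.

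**4. The two C-SSRS rules.** Take a youth who does not report current planning. The first sentence of the row gives that youth the C-SSRS; the last sentence does not. The row's header, with four administrations each following a survey, favours the first. Section 11 escalates either planning or a recent attempt, whereas the restrictive sentence is triggered by planning alone. A youth reporting a recent attempt without current planning would be escalated, but the row would not call for the C-SSRS.

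**5. Time for a universal C-SSRS.** At the stated 5 minutes each: 215 × 5 / 60 = 17.9 h; 245 × 5 / 60 = 20.4 h.

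**The case against.** Five points can be made for the plan.

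- **The absence is read from an imperfect text.** The suicidality bullet in Table 2, directly after depression, reads as if an instrument name had run into a separate item. The C-SSRS row relies on a planning screen that is not readable in the survey either. An anxiety line could have been lost there. This stands as a reason for medium confidence. Against it, the remaining domains have intact labels and instruments, and no anxiety scale is named anywhere else.
- **The monitoring plan may settle the C-SSRS rule.** Section 16 (Data and Safety Monitoring Plan) refers to an attachment that was not available. This also stands, but the table row would still need correcting to match it.
- **The safety consequence is limited.** Responses are reviewed immediately after each assessment, and reported planning or a recent attempt goes to the responsible clinician under either rule. This is correct and limits the point to who receives the structured assessment.
- **Anxiety is one descriptive, distal outcome.** Aims 1 and 2 and the power calculation are untouched. That is true and keeps the severity moderate, but the output is promised in the aim and twice more in Section 4.
- **Coverage of the other outcomes may be less than complete.** Section 9 says only selected questionnaires are repeated after baseline, without naming them. Table 2 nevertheless assigns the youth survey, including depression and suicidality, to four occasions.

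**Conclusion.** Both parts hold. As written, the plan cannot produce the anxiety estimate that Aim 3 promises: one of four named outcomes has no measure, over roughly 215 to 245 youth surveys. No error rate or power is affected, because Aim 3 is descriptive. The C-SSRS row contains two incompatible rules, and neither Table 1 nor Section 11 resolves them. Ideation and attempts remain covered by the youth self-report items, and escalation does not depend on which rule is used. The plan should be changed on both points, but neither undermines the trial. The conclusion assumes that the readable Table 2 is complete for anxiety and that the monitoring plan does not already state a single C-SSRS rule. The survey count assumes the enrolment and completion pattern set out in the working.

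**What to change.** 1. **Anxiety.** Add a short paediatric anxiety form from the PROMIS family, already used for depression, to the youth survey at all four assessments. This costs a few minutes per survey and no extra visit. Otherwise, delete anxiety from Aim 3 and from both places in Section 4, which is a change of wording only.
2. **C-SSRS.** Keep one rule, consistent with the monitoring plan. The better choice is all youth after every survey: the row's first sentence already commits to it, and it takes about 18 to 20 staff hours over the study. If it stays conditional, trigger it on a recent attempt as well as current planning, to match Section 11.
3. **Source of rates.** State in Section 17 that Aim 3 ideation and attempt rates come from the self-report items given to every youth, so that they do not depend on the C-SSRS rule.
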